5.9 Software to be used for Analyses

All analyses performed by Emmes will use SAS[®] Version 9.3 or higher software.

6 STUDY SUBJECTS

6.1 Participant Disposition

The disposition of participants and exposure to study vaccinations will be tabulated by site and treatment group.

6.2 Protocol Deviations

A summary of participant-specific protocol deviations will be presented by the reason for the deviation, the deviation category, and treatment group for all participants. All participant-specific protocol deviations and non-participant-specific protocol deviations will be included as data listings. Protocol deviations will not necessarily always lead to exclusion from the analysis population. Determination of exclusion will be established before breaking the blind and based on the blinded review of protocol violations.

7 STATISTICAL ANALYSIS

Descriptive statistics (mean, standard deviation, median, range) for continuous measures (e.g., age) and proportions for categorical measures (e.g., gender) will be summarized by treatment group. All percentages will be presented to one decimal place. Means, medians, standard deviations, confidence intervals, etc., will be presented as integers if the absolute value is greater than or equal to 100 in magnitude, to one decimal place if greater than or equal to 10, and 2 decimal places if less than 10. P-values will be reported to 4 decimal places.

For both safety and immunogenicity, when the use of descriptive statistics to assess group characteristics or differences is required, the following methods will be used: for categorical variables/responses, the number, proportion (% and exact 95% confidence interval) of participants in each category. For continuous variables/responses, the mean, median, standard deviation, quartiles and range, as well as the geometric mean and 95% confidence interval for immunogenicity outcomes. A non-parametric method (e.g., bootstrap or Wilcoxon rank sum test) will be used for continuous variables if the data are not consistent with the normal distribution.

The following methods will be used for formal testing of differences between study groups: for binomial response variables logistic regression will be used to test for an overall treatment effect and, if statistically significant, p-values from all pair-wise comparisons obtained from the regression model will be reported. Where multiple results are available for the same participant (e.g., reactogenicity after each vaccination), the correlation between results from the same participant will be taken into account by using a generalized mixed effects model, with treatment group as a fixed effect and participant as a random effect. For continuous variables that are not normally distributed, the overall treatment effect will be assessed by the Kruskal-Wallis test and if statistically significant, pair-wise comparisons will be performed using the Wilcoxon 2-sample test. For \log_{10} immunogenicity values the overall treatment effect will be assessed by ANOVA and if statistically significant, estimates of all pair-wise comparisons from the model will be reported.

All testing and inference will be performed with a 2-sided p-value of 0.05. For each immunogenicity endpoint, a multiplicity adjustment for 4 treatment groups will be applied using a sequential testing approach by performing an overall comparison of all treatment groups prior to pair-wise comparisons. No multiplicity adjustment for multiple immunogenicity endpoints is planned, since the dose selection for the Phase 3 will be based on comprehensive statistical and clinical evaluation of all immunogenicity endpoints including safety results.

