3.2 STUDY SCHEMA

Group		Trivalent P2-VP8 Dose	N	-7 ^a to -1	0	7	28	56	84	89, 91, 93	168	224
A Adult	A1	30 µg	12	B(S,I)	X	B(S)	X, B(I)	X, B(I)	B(I)			F
		Placebo	3	B(S,I)	P	B(S)	P, B(I)	P, B(I)	B(I)			F
	A2	90 µg	12	B(S,I)	X	B(S)	X, B(I)	X, B(I)	B(I)			F
		Placebo	3	B(S,I)	P	B(S)	P, B(I)	P, B(I)	B(I)			F
A Total			30									
B Toddler	B1	30 µg	12	B(S,I)	X	B(S)	B(I)				F	
		Placebo	3	B(S,I)	P	B(S)	B(I)				F	
	B2	90 µg	12	B(S,I)	X	B(S)	B(I)				F	
		Placebo	3	B(S,I)	P	B(S)	B(I)				F	
B Total			30									
C Infant	C1	15 µg	12	B(S,I)	X	B(S)	X	X, B(I)	B(I)	Sh		F
		Placebo	4	B(S,I)	P	B(S)	P	P, B(I)	B(I)	Sh		F
	C2	30 µg	12	B(S,I)	X	B(S)	X	X, B(I)	B(I)	Sh		F
		Placebo	4	B(S,I)	P	B(S)	P	P, B(I)	B(I)	Sh		F
	C3	90 µg	12	B(S,I)	X	B(S)	X	X, B(I)	B(I)	Sh		F
		Placebo	4	B(S,I)	P	B(S)	P	P, B(I)	B(I)	Sh		F
C Total			48									
D Infant		15 µg	138	B(S,I)	X		X	X, B(I)	B(I)	Sh		F
		30 µg	138	B(S,I)	X		X	X, B(I)	B(I)	Sh		F
		90 µg	138	B(S,I)	X		X	X, B(I)	B(I)	Sh		F
		Placebo	138	B(S,I)	P		P	P, B(I)	B(I)	Sh		F
D Total			552									
All Cohorts Total			660									

X = Trivalent P2-VP8 vaccine

P = placebo

B = blood sample for (S) safety and/or (I) immunogenicity testing

F = final study f/u visit/call

Sh = stool samples to assess Rotarix shedding. Only at RMPRU (Soweto).

^aFor adult and toddler cohorts, -28 to -1

For each age group, progression from one dose level to the next will require review of clinical and safety lab data through 7 days after the first dose at the lower dose level. Safety laboratory blood specimens will be drawn at baseline for all participants (screening) and 7 days after first study injection in Groups A, B and C.

[figure not shown]
Blood samples for immunogenicity analysis will be obtained at baseline for all participants, Days 28, 56 and 84 for Group A (adults), Day 28 for Group B (toddlers), and Days 56 and 84 for Groups C and D (infants).

Stool samples to assess Rotarix shedding will be obtained from infants (Groups C and D) on days 89, 91 and 93 (i.e., 5, 7 and 9 days after the first Rotarix dose on day 84) in the subset of infants enrolled at the Respiratory and Meningeal Pathogens Research Unit (RMPRU).

For each dose level, progression from adults in Group A to toddlers in Group B and then to infants in Group C will require review of clinical and safety laboratory data through 7 days after study injection in the older group. (see Figure 1)

These determinations will be made by the Safety Review Committee (SRC).

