4 SAMPLE SIZE CONSIDERATIONS

4.1.1 Primary Safety Endpoints

Safety will be assessed by analyses of the following primary endpoints (events), where the unit of analysis in each case will be the proportion of participants with at least one event:

- Moderate or greater solicited local reactions
- Moderate or greater solicited systemic reactions
- Moderate or greater adverse events
- Moderate or greater adverse events where there is a reasonable possibility that the study product caused the event, i.e., are suspected adverse reactions
- Serious adverse events

It was assumed that almost all participants enrolled would provide data for safety analysis and at least 90% of enrolled participants would be evaluable for immunogenicity assessments.

Safety

The sample size for this study was selected to detect frequent adverse events. Given a planned sample size of 12 vaccine recipients per dose group and 24 vaccine recipients for the two dose groups combined in both adults and toddlers (A and B), the study will have an approximately 90% chance of observing at least one AE that occurs at a rate of 17.5% and 9.2%, respectively. For the two infant cohorts combined (C and D), 150 vaccine recipients per dose group and 450 vaccine recipients for the three dose groups combined will provide at least 90% chance of observing an AE that has a 1.6% and 0.5% rate of occurrence, respectively.

Conversely, if no SAEs are observed in 24 and 450 vaccine recipients, the study will be able to rule out SAEs occurring at a rate of approximately 11.7% and 0.7%, respectively based on the upper bounds of the one-sided 95% confidence.

Primary Immunogenicity Endpoints

Based on the results in South African infants who received monovalent P2-VP8 vaccine or placebo (VAC-013), the strain specific seroresponse rates for both P2-VP8 vaccine doses were expected to be $\geq 80\%$ for at least one of the three P2-VP8 vaccine doses and $<20\%$ for the placebo group. For the two infant cohorts combined, with 135 evaluable recipients per dose level (assuming 10% loss), this study was designed to provide at least 74% and 95% power (Fisher's exact 2-tailed test) to detect 15 and 20 percentage points

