5.4 Covariates and Subgroups

There is no *a priori* plan to summarize the immunogenicity or safety endpoints for covariates. The protocol is set up as a descending age-group study, so each age-group will be summarized separately. The 3 age groups to be analyzed are adults (18-45 years), toddlers (2 to <3 years) and infants (6 to <8 weeks). Safety endpoints for infants will be presented for each site and for all sites combined.

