Neutralizing antibody Fold-Rise (FR) from Pre-Vaccination will be presented by treatment and time-point. This analysis will be separately presented for adults, toddlers and infants and each rotavirus strain (Wa, DS-1 and 1076) as well as heterologous strains. An ANOVA or Kruskal-Wallis test will be conducted to assess the difference between treatment groups in mean log (base10) FR. Separate p-values will be presented at each time-point. Two-sided 95% CI for the geometric mean fold rise for each treatment group will be obtained using a t-distribution on log transformed fold rise measurements. For infants, analysis will be conducted two ways 1) Unadjusted for Maternal Antibodies 2) Adjusted for Maternal Antibodies.

Number and Proportion of subjects with neutralizing antibody response (at least a 2.7-fold and a 4-fold rise in neutralizing antibody titers from baseline) will be presented by treatment and time-point. This analysis will be separately presented for adults, toddlers and infants; and each of the three rotavirus strains (Wa, DS1, 1076) as well as heterologous strains. The proportion of participants with a positive response at a specific time point will be evaluated using the 2-sided exact binomial (Clopper-Pearson) 95% CI for each treatment group. A logistic regression analysis will be performed to test the overall treatment effect. Separate p-values will be presented at each time-point. For infants, analysis will be conducted two ways 1) Unadjusted for Maternal Antibodies 2) Adjusted for Maternal Antibodies.

Number and Proportion of subjects with a neutralizing antibody response against at least **2 of the 3** rotavirus strains (Wa, DS1, 1076), against all 3 rotavirus strains and against each of the 3 specific pairs of rotavirus strains will be presented by treatment group and time-point. The proportion of participants with a positive response at a specific time point will be evaluated using the 2-sided exact binomial (Clopper-Pearson) 95% CI for each treatment group. A logistic regression analysis will be performed to test the overall treatment effect. Separate p-values, estimates and 95% confidence intervals from the logistic regression will be presented at each time-point. For infants, analysis will be conducted two ways 1) Unadjusted for Maternal Antibodies 2) Adjusted for Maternal Antibodies.

Analysis of Anti-rotavirus IgA Responses to Whole Viral Lysate

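### The infant IgG and neutralizing responder models leave out the baseline titer: the analysis is valid and unbiased, but it may give up power in between-dose comparisons

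*SAP*

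**What the plan says.** Section 7 gives the general rule: "for binomial response variables logistic regression will be used to test for an overall treatment effect", with pairwise p-values taken from the same model if the overall test is significant. Section 7.1.4 applies it to IgG and IgA seroresponse, to each strain-specific neutralizing response and to the 2-of-3-strain endpoint: "A logistic regression analysis will be performed to test the overall treatment effect". No other model term is named. Section 5.4 adds that there is no a priori "plan to summarize the immunogenicity or safety endpoints for covariates".

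A seroresponse is at least a 4-fold rise over the participant's own baseline; a neutralizing response is at least a 2.7-fold (also 4-fold) rise. The baseline is available throughout: "Blood samples for immunogenicity analysis will be obtained at baseline for all participants" (section 3.2).

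For infants, section 7.1.4 also plans a second analysis of IgG and neutralizing responses that corrects the fold-rise for maternal-antibody decay, FRMA = (Td/T0) × 2^(d/MH), with one half-life MH per assay.

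On power, section 4.1.1 (under Primary Immunogenicity Endpoints) works "with 135 evaluable recipients per dose level (assuming 10% loss") and claims "at least 74% and 95% power (Fisher's exact 2-tailed test) to detect 15 and 20 percentage points", with 65% vs 80% and 60% vs 80% as examples. For a 2-fold GMT difference it claims at least 98%.

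**The concern.** A responder is defined by post titer divided by baseline titer. An infant who starts high on maternal antibody therefore tends to need a higher later titer to qualify. Unless log post titer rises one-for-one with log baseline, baseline predicts response, and a logistic model with that predictor can separate the dose groups more sharply.

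The decay correction does not do this job. At a given visit d is nearly the same for all infants and MH is one number per assay, so every fold-rise is multiplied by almost the same factor. That moves the cut-off; it does not use the infant's own baseline as a predictor.

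At stake is precision in the between-dose responder comparisons, which are one input to the Phase 3 dose choice (sections 5.8 and 7). Among the stated immunogenicity power figures, the 15-point dose difference has the lowest.

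**Working it through.** **Inputs from the SAP.** 135 evaluable per dose level (150 × 0.90); two-sided 0.05 ("All testing and inference will be performed with a 2-sided p-value of 0.05"); 65% vs 80%; log10 SD between 0.24 and 0.56, quoted for the GMT calculation and not identified as baseline or post-vaccination.

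**Assumption.** The SAP gives no correlation rho between baseline and Day 84 log titer and no ratio of the two SDs, so both are varied.

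**1. The plan's own figures.** Exact enumeration of Fisher's two-sided test at 135 per group gives 75.3% for 65% vs 80% (stated: at least 74%) and 93.9% for 60% vs 80% (stated: 95%). Both agree within 2 points.

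**2. Power of the planned test.** The analysis is logistic regression, not Fisher's test. The pooled z formula gives 79.1% for 65% vs 80%, and simulated likelihood-ratio tests give 79-81%.

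**3. How strongly baseline predicts response.** With baseline SD s0, post SD s1 and correlation rho:

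- slope of log post on log baseline = rho × s1/s0
- correlation of baseline with a lower fold-rise, r = (s0 − rho·s1) / √(s0² + s1² − 2·rho·s0·s1)

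For example, with s0 = s1 and rho = 0.5, r = √((1 − 0.5)/2) = 0.50. With s0 = 0.40, s1 = 0.56 and rho = 0.5, r = (0.40 − 0.28)/√0.2496 = 0.24.

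**4. Power with and without log10 baseline.** Two dose groups of 135; baseline and post titer bivariate normal on log10; 4-fold cut-off; arm means set to give 65% and 80%; likelihood-ratio test of treatment. Post SD is 0.56 throughout.

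| Baseline SD | rho | slope | r | Without | With |
|---|---|---|---|---|---|
| 0.56 | 0 | 0 | 0.71 | 79.9% | 92.8% |
| 0.56 | 0.25 | 0.25 | 0.61 | 79.6% | 88.6% |
| 0.56 | 0.5 | 0.5 | 0.50 | 79.9% | 84.9% |
| 0.56 | 0.75 | 0.75 | 0.35 | 80.8% | 83.5% |
| 0.40 | 0.5 | 0.70 | 0.24 | 79.6% | 80.0% |
| 0.30 | 0.5 | 0.93 | 0.04 | 79.3% | 79.0% |
| 0.24 | 0.5 | 1.17 | −0.08 | 79.0% | 79.2% |

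The 0.40 and 0.30 rows use 2,000 simulated trials and the others 4,000. The Monte Carlo standard error is about √(0.8 × 0.2/4,000) = 0.6 points, or 0.9 points with 2,000, so the 0.3-point fall in the 0.30 row is noise. The largest gain is 92.8 − 79.9 = 12.9 points.

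Setting r directly gives the same picture: 78.9% to 81.5% at r = 0.3, 78.8% to 84.4% at 0.5, and 79.1% to 91.5% at 0.7. By the two-proportion formula, those adjusted powers correspond to unadjusted groups of about 144, 155 and 195 instead of 135.

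**5. Type I error.** With both arms at 65% it is 4.6-5.7% without and 4.7-5.8% with baseline.

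**6. The larger contrast.** For 60% vs 80% at r = 0.5, power goes from 95.6% to 97.6%.

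**7. The decay correction.** At d = 84 with an assumed half-life of 21 to 60 days, the factor is 2^(84/21) = 16 to 2^(84/60) = 2.6. The 4-fold rule becomes Td/T0 ≥ 4/16 = 0.25 to 4/2.6 = 1.5, the same for all infants whatever their baseline.

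**The case against.** The strongest reply is that this is a design preference and not an error: the SAP says openly that it plans no covariates, nothing in it contradicts that, and randomization protects the comparison. That stands, and it limits the point to an optional gain in efficiency.

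The second reply is that the gain rests on quantities the SAP does not give. That also stands. Within the quoted SD range, a baseline SD of 0.40 against a post SD of 0.56 at rho 0.5 already removes the benefit. Section 3.4.2 also replaces values below the LLOQ with a single number. If 50% of baselines were below it (an assumption; equal SDs, rho 0.5), the simulated gain is about 3 points (80.3% to 83.5%). What survives is that adjustment cost no power beyond simulation noise in any scenario run.

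Third, a reader might infer that the planned test has only 74% power and that the covariate makes up the shortfall. The documents do not support that. The 74% is a lower bound for Fisher's exact test, and the logistic test starts about 5 points higher.

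Fourth, a reader might infer that the primary neutralizing hypothesis is at stake. It is not. That hypothesis asks whether 60% or more respond to at least 2 of 3 strains in at least one group, and is read from within-arm proportions with Clopper-Pearson intervals. A covariate does not change those.

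**Conclusion.** The point holds as an efficiency improvement. The infant IgG and neutralizing logistic models contain only treatment, although the response is scored against a baseline titer collected for everyone. The analysis is valid and unbiased as written; a reading that it is biased or invalid has no support in the documents.

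For 65% vs 80% with 135 per arm, power could rise from about 79-80% by roughly 0 to 13 points, with type I error near 5%. This range assumes bivariate normal log titers, rho from 0 to 0.75 and a baseline SD no larger than the post SD. A baseline more variable than the Day 84 titer could give more, but nothing in the SAP shows that to be the case. A claim that the gain is at least 5 points would be too strong: it is 2.7 points at rho 0.75 with equal SDs and about none when the baseline SD is modestly smaller. For a 20-point difference there is little left to gain.

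**What to change.** In sections 7 and 7.1.4, before unblinding:

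- Add log10 baseline titer of the same assay and antigen or strain as a covariate in the infant logistic models for single-antigen IgG seroresponse and single-strain neutralizing response. Take the overall and pairwise p-values from that model.
- Report the difference in response rates standardised over the pooled baseline distribution beside the odds ratio, because the adjusted odds ratio is conditional on baseline.
- Keep the treatment-only model as a sensitivity analysis, and keep the Clopper-Pearson rates by arm.
- For the 2-of-3-strain endpoint, the three strain-specific log10 baselines may be added, provided no infant whose status is already determined is lost. An infant missing one baseline who responds to both other strains is a responder, and one who responds to neither is a non-responder. A missing-baseline indicator or a mean-imputed baseline keeps both. This three-baseline model was not simulated here.

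IgA can stay as it is: the SAP's own maternal-antibody concern covers only IgG and neutralizing antibody.

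The cost is SAP wording, one extra model term (three for the 2-of-3 endpoint) and a short standardisation step. No new data are needed.

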3.3.4 Method of Assigning Participants to Treatment Groups (Randomization)

Enrollment is sequential in the order given below and in the group sample sizes given in Table 3.3.4.

Cohort A1: Adults were randomly assigned to 30 µg P2-VP8 or Placebo in a 4:1 ratio.

Cohort A2: Adults were randomly assigned to 90 µg P2-VP8 or Placebo in a 4:1 ratio.

Cohort B1: Toddlers were randomly assigned to 30 µg P2-VP8 or Placebo in a 4:1 ratio.

Cohort B2: Toddlers were randomly assigned to 90 µg P2-VP8 or Placebo in a 4:1 ratio.

Cohort C1: Infants were randomly assigned to 15 µg P2-VP8 or Placebo in a 3:1 ratio.

Cohort C2: Infants were randomly assigned to 30 µg P2-VP8 or Placebo in a 3:1 ratio.

Cohort C3: Infants were randomly assigned to 90 µg P2-VP8 or Placebo in a 3:1 ratio.

Cohort D: Infants were randomly assigned to 15 µg, 30 µg or 90 µg of P2-VP8, or to Placebo in a 1:1:1:1 ratio.

Table 3.3.4 Dosing Schedule

Group	P2-VP8 dose	N	Study Day		
			0	28	56
A Adults	30 µg	12	X	X	X
	Placebo	3	X	X	X
	90 µg	12	X	X	X
	Placebo	3	X	X	X
B Toddlers	30 µg	12	X		
	Placebo	3	X		
	90 µg	12	X		
	Placebo	3	X		
C Infants	15 µg	12	X	X	X
	Placebo	4	X	X	X
	30 µg	12	X	X	X
	Placebo	4	X	X	X
	90 µg	12	X	X	X
	Placebo	4	X	X	X
D Infants	15 µg*	138	X	X	X
	30 µg*	138	X	X	X
	90 µg*	138	X	X	X
	Placebo	138	X	X	X

X = Injection day

* If dose tolerated in Group C

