difference (e.g. 65% vs. 80% and 60% vs. 80%), respectively, in seroresponse rates between any two P2-VP8 dose groups. For comparisons with the combined placebo groups, this study was designed to provide $\geq 99\%$ power (Fisher's exact 1-tailed test) to detect a ≥ 30 percentage point increase in the P2-VP8 group compared with placebo (e.g. 50% vs. 20%).

For the sample calculations of the Geometric Mean Titer (GMT) endpoint based on the VAC 013 study, the LOG_{10} standard deviations were estimated to be <0.6 (range: 0.24 – 0.56) for the P2-VP8 doses and the placebo group. Using a conservative LOG_{10} standard deviation (SD) of 0.6, this study with 135 evaluable infants per group (assuming 10% loss) was designed to provide at least 98% power to detect as low as a 2-fold difference between any two P2-VP8 dose groups or between any P2-VP8 vaccine dose (15 μg , 30 μg or 90 μg dose) and the placebo group.

i.e., for 2 groups A & B, with A > B:

$$\text{Require } \text{GMT(A)} / \text{GMT(B)} \geq 2$$

$$\text{i.e., } \text{Log}_{10}\text{A} - \text{Log}_{10}\text{B} \geq \text{Log}_{10}(2) \approx 0.301$$

$$\text{Therefore, } \text{A} \sim \text{N}(\mu, 0.6) \text{ and } \text{B} \sim \text{N}(\mu - 0.301, 0.6)$$

Under this assumption using a student t-test, a sample size of N=135 (per group) will give 98% power to detect a significant difference at the 5% level in mean Log_{10} titer between 2 groups of at least 0.301.

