5.7 Multicenter Studies

This study is being conducted at 3 sites: the Respiratory and Meningeal Pathogens Research Unit (RMPRU) in Soweto enrolled all participants in groups A to C. Group D infants were enrolled at 3 sites: RMPRU, SRC (Shandukani Research Centre) and FAM-CRU (Family Clinical Research Unit, Tygerberg). All summary tables, graphs and listings for infants in groups C and D will be reported by site and for all 3 sites combined.

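### Infant cohorts randomised separately and in sequence are pooled with no cohort term (small effect), and the adult and toddler 30 vs 90 µg contrast is wholly non-randomised

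*SAP*

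**What the plan says.** **Randomisation (Section 3.3.4).** "Enrollment is sequential in the order given below and in the group sample sizes given in Table 3.3.4". Cohorts A1, A2, B1 and B2 each allocate one dose or placebo 4:1 (12 and 3). Each of C1 to C3 allocates one dose level of "P2-VP8 or Placebo in a 3:1 ratio" (12 and 4). Group D allocates 15, 30, 90 µg and placebo 1:1:1:1, 138 per arm.

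**Sites (Section 5.7).** One site, RMPRU, "enrolled all participants in groups A to C". Group D came from three sites. Section 3.2 restricts stool sampling to RMPRU.

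**Pooling (Section 4.1.1).** Power is stated as "For the two infant cohorts combined, with 135 evaluable recipients per dose level" and "For comparisons with the combined placebo groups". Section 7.1.4 also runs the maternal-antibody-adjusted analyses on the combined infant cohorts.

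**Models (Sections 5.8 and 7).** An overall test across treatment groups comes first, by logistic regression, ANOVA or Kruskal-Wallis. For binary responses, "if statistically significant, p-values from all pair-wise comparisons obtained from the regression model will be reported"; the other methods have equivalent pairwise steps. The mixed model has treatment as its fixed effect and participant as its random effect. No cohort term is named in any between-group model.

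**The concern.** Randomisation protects a comparison only between people allocated together. The 12 Group C infants in each dose arm were never randomised against another dose, and the pooled placebo group contains infants from cohorts other than theirs. A change between cohorts in season, natural exposure, maternal antibody or site mix can then enter the dose estimates. The SAP itself treats such factors as relevant: the note to Figure 1 refers to delaying infant enrolment until after the rotavirus peak, and Section 7.1.4 allows for community infection and maternal antibody.

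In adults and toddlers each dose is its own cohort, so the dose contrast is the cohort contrast, yet the plan attaches a p-value to it. Sections 5.8 and 7 say that the results feed the choice of dose for Phase 3.

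**Working it through.** **1. The plan's own figures.** 150 × 0.9 = 135 evaluable per arm. Two-sided Fisher power by full enumeration is 75.3% for 65% vs 80% (stated: at least 74%) and 93.9% for 60% vs 80% (stated: 95%). The t-test for a 0.301 log10 difference with SD 0.6 gives 98.4% (stated: 98%). All agree to within about a point.

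**2. Share of each infant arm from Group C.** 12/(12 + 138) = 8%, so 92% of each arm is randomised concurrently. The 12 Group C placebo infants are spread 4/4/4.

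**3. Infant bias = share × cohort shift.** The SAP gives no shift, so these are assumptions.
- Dose vs dose, 20 points between C cohorts: 0.08 × 20 = 1.6 points. At an 80% response rate, SE = √(2 × 0.8 × 0.2/135) = 0.0487, and a 5% test rejects 6.2% of the time. A 10-point shift gives 5.3%; a 40-point shift gives about 10%.
- Dose vs dose, 2-fold titre shift: 10^(0.08 × 0.301) = 1.06 in the GMT ratio. SE = 0.6 × √(2/135) = 0.073; rejection is 6.3%.
- Dose vs placebo, one C cohort deviating by 20 points: (12/150 − 4/150) × 20 = 1.1 points.

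**4. Shedding subset.** All of Group C is at the stool-sampling site; Group D's number there is not given. Assumptions: a 20-point shift and a 30% shedding rate, with SE = √(2 × 0.3 × 0.7/n).

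| Group D per arm at site | Group C share | Bias | Rejection of a 5% test |
|---|---|---|---|
| 30 | 12/42 = 29% | 5.7 points | 8.8% |
| 46 (one third of 138) | 12/58 = 21% | 4.1 points | 7.7% |
| 100 | 12/112 = 11% | 2.1 points | 6.4% |

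**5. Adults and toddlers, 30 vs 90 µg, 12 vs 12.** The share is 100%. SE = 0.6 × √(2/12) = 0.245. By noncentral t on 22 df, shifts of 0.1, 0.2 and 0.3 log10 give 6.8%, 12.2% and 21.6% rejection with no dose difference. This borrows the SAP's SD of 0.6, which was set for infants.

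The overall-test gate was then simulated with 12/12/6, SD 0.6, and placebo recipients shifting with their cohort. If both doses exceed placebo by 1.0 log10, gated rejection is 6.8%, 12.3% and 21.6%. If the vaccine has no effect, it is about 3.7%, 7.1% and 13.5%.

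**6. Cost of a cohort term (linear model).** Each C cohort contributes 12 × 4/16 = 3 units of within-cohort information on its own dose.
- Dose vs dose: variance 2/(138 + 3), so effective n = 141 × 0.9 = 126.9.
- Dose vs placebo: the information matrix for the three dose effects is 141·I − 34.5·J, where I is the identity, J is all ones and 34.5 = 138²/552. The variance is (37.5 + 34.5)/(141 × 37.5) = 0.01362, where 37.5 = 141 − 3 × 34.5. Effective n = (2/0.01362) × 0.9 = 132.2.
- Dose-dose power at n = 127: 72.8%, 92.5% and 97.9%. Group D alone (138 × 0.9 ≈ 124): 71.4%, 91.7% and 97.6%.

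**The case against.** The strongest reply is that the primary infant analysis is barely touched. Ninety-two percent of each arm is concurrently randomised, and 1.6 points is small beside the 15 to 20 points the trial is powered for. Escalation rests on one week of safety data, so cohorts may be only weeks apart, and C1 to C3 share one site; a 20-point or 2-fold shift may be near the worst case. This stands. A reader might infer that the infant comparisons are generally non-randomised, and the documents do not support that.

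Two other readings go too far. Treatment as the sole fixed effect is stated only for the mixed model; the logistic and ANOVA terms are not listed. The absence in Section 5.4 of any a priori "plan to summarize the immunogenicity or safety endpoints for covariates" concerns summaries, and does not prohibit an adjusted model. What remains is that no model names cohort. Pooling of placebo recipients is explicit for infants but only implied for adults and toddlers; the 30 vs 90 µg contrast does not depend on it.

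The gate does lower the adult and toddler error rates, but only when the vaccine effect is too weak to open it. Tables by cohort (Sections 7.1.1 and 7.1.2) and by site (Section 5.7) make differences visible without adjusting any estimate. Shedding is exploratory and adult and toddler immunogenicity is secondary, which limits the consequence.

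Cohort strata can also cause separation in logistic models for rare safety events, and a stratified two-group rank test would not replace the four-group Kruskal-Wallis test. Both points narrow the remedy.

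**Conclusion.** The point holds, with a size that depends on the age group. For the primary infant analysis it is minor: 8% of each dose arm, with about 6% type I error under an assumed 20-point or 2-fold shift. For shedding it may be larger, about 2 to 6 points over an assumed 100 to 30 Group D infants per arm at the one site. For adults and toddlers any shift passes in full into the 30 vs 90 µg contrast; the rejection rates of about 7%, 12% and 22% apply when both doses exceed placebo enough to open the gate. Every shift is an assumption. The case for change rests on analysing by the units that were randomised, at little cost, and not on evidence that a shift occurred.

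**What to change.** - **Infants:** in Sections 7, 7.1.4 and 7.1.5, include randomisation cohort (C1, C2, C3, D) as a fixed term in the ANOVA and logistic models for immunogenicity and shedding. Each C cohort then contributes only its own dose-versus-concurrent-placebo contrast.
- **Where that is unworkable** (rank tests, sparse safety events): repeat the comparison in Group D alone.
- **Groups A and B:** report 30 vs 90 µg descriptively, labelled as a non-randomised between-cohort comparison, without a p-value.

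The cost is SAP wording and one class variable with 3 degrees of freedom. Effective n per arm falls from 135 to about 127 (dose-dose) or 132 (dose-placebo). Dose-dose power for 65% vs 80% moves from 75.3% to 72.8%, and for a 2-fold GMT difference from 98.4% to 97.9%. The adult and toddler dose-dose p-values are lost.
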